5. METHODOLOGY

5.1. Feasibility Assessment

Prior to conducting this study, two feasibility assessments were conducted to support the study objectives including a preliminary feasibility assessment and more refined assessment following cohort selection. The feasibility informs on the number of patients in each pre-defined group of new users of respiratory medications and the number of patients meeting different definitions of pneumonia. These figures will allow for an assessment of the available statistical precision to examine treatment group differences.

Mannino and colleagues found a rate of pneumonia requiring hospitalization to be 22.7 per 1,000 person years among patients with advanced disease (GOLD stage airflow limitation III or IV) [Mannino, 2009]. A previous study of community-acquired pneumonia (CAP) in a primary care population of patients with COPD in the GPRD [Müllerova, 2012], there were approximately 40,000 patients with prevalent COPD in CPRD-GOLD between 1996-2006 with ~8% experiencing pneumonia (CAP without restricting to those requiring hospitalization) during the study period with a CAP rate of 22.4 per 1000 person years. The authors included a highly sensitive definition of pneumonia, resulting in 1,469 cases of CAP in their case-control study.

Feasibility results on the 2005-2010 study period included approximately 12,000 new users and 185 pneumonia events. When expanding to include the study period 2002-2010, there will be approximately 18,742 new users of ICS-containing medications (n=12,065) or long-acting bronchodilators (LABD) based on requiring CPRD-GOLD linkage to HES, and hospitalization data 12-mo prior to the new user prescription as presented in Table 1. These totals include the application of all inclusion/exclusion criteria; however, additional subjects may get excluded in the final analysis based on censoring and on-going pneumonia at the time of cohort entry.

Number		F	1	Year o	f Cohort	Entry	F			
of New	0000	0000	0004	0005	0000	0007	0000	0000	0040	T - 4 - 1
Users	2002	2003	2004	2005	2006	2007	2008	2009	2010	lotal
LABD	354	513	703	765	715	723	972	938	994	6,677
ICS-										
containing ^a	1,828	1,499	1,633	1,369	1,310	1,207	1,244	1,100	875	12,065
Total by										
Year	2,182	2,012	2,336	2,134	2,025	1,930	2,216	2,038	1,869	18,742

Table 1 Feasibility Results: New User Cohort

 ICS-Containing=inhaled corticosteroid-containing medications, LABA=long-acting beta-agonists, LAMA=longacting antimuscarinics

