5.2.2. Inclusion / Exclusion Criteria

Inclusion Criteria

Patients are required to:

- 1. Have CPRD-GOLD data of acceptable research quality according to CPRD standards.
- 2. Be new users of LABD or ICS-containing medications from January 2002-December 2010
- 3. Have a COPD diagnosis at any time in the period prior to and including the Cohort Entry Date (to eliminate any patients with asthma only)
- 4. Have at least one year of data prior to Cohort Entry Date.
- 5. Be at least 45 years of age at Cohort Entry Date.
- 6. Have GPRD-HES linkage. (Note: these individuals need to be retained for basic demographics but are not part of the new user cohort).
- 7. Have HES coverage one year prior to the Cohort Entry Date

Exclusion Criteria

1. Patients with an occurrence of a code for a medical condition incompatible with COPD diagnosis any time in their history. This list contains conditions that are a related to lung or bronchial developmental anomalies, degenerative processes (cystic fibrosis, pulmonary fibrosis), bronchiectasis, pulmonary resection or other significant respiratory disorders other than COPD (but not including cancer) that can interfere with clinical COPD diagnosis or substantially change the natural history of the disease.

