5.6. Confounders

Key risk factors for pneumonia that may also relate to treatment will be measured in the one-year Baseline Period. For the purposes of general co-morbidity assessment and vaccination for pneumonia, a longer history will be examined. Although patients may have varying periods of history, this is not expected to be differentially recorded by treatment (which could result in information bias). A longer look back period is needed to identify co-morbidities given they may not be recorded in the Baseline Period.

Confounders that are based on "counts" of healthcare encounters and exacerbation will be categorized during analysis (e.g., tabular summaries, propensity score creation, Cox modeling).

Variable	Parameterization
Age at Cohort Entry	Age will be treated either as a continuous variable, or as a categorical one (see Table shells for intervals)
Gender	Male=1 or Female=0
Body Mass Index (BMI) during Ever in Patient History	Weight in kilograms divided by height in meters squared, will be utilised as a categorical variable using the following categories widely referenced as WHO classification: Underweight (Below 18.5), Normal (18.5 - 24.9), Overweight (25.0 - 29.9), and Obese (30.0 and greater).
	For modelling, the following cutoff values will also be examined: BMI<21, BMI 21-24.9, BMI ≥25.
Smoking status during Ever in Patient History	Four categories will be created: ex-smoker, current smoker, non-smoker, and unknown smoking status containing patients with missing entries or other types of tobacco exposure (e.g. passive smoking). Non-smoker will be the referent group in modelling.
Overall Social Deprivation Scores for England	The deprivation quintile is derived the 32,482 areas of social deprivation, with 1 being most deprived and 32,482 being least deprived. quintiles will be identified as follows (with least deprived the referent in modelling). Quintiles are provided by CPRD:

Variable	Parameterization
Townsend Scores	Quintile. Townsend scores will be described by quintile, as provided by CPRD-GOLD.
Charlson Co-morbidity index and individual chapters Ever in Patient History (prior to Cohort Entry Date)	Charlson's comorbidity index chapter indicator measures will be created using a recently published algorithm by Khan and colleagues [Khan, 2010] after removing COPD and AIDS from the disease list. Some patients may have COPD and some may not (incident diagnosis). AIDS will be excluded due to very low prevalence in the general population.

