	• 31 = Maternity: where the baby was delivered after the mother's admission
	• 32 = Maternity: where the baby was delivered before the mother's admission
	• 81 = Transfer of any admitted patient from another hospital provider other than in an emergency; this does not include admissions to high security psychiatric hospitals (HSPH)
	• 82 = Other: babies born in health care provider
	• 83 = Other: babies born outside the health care

Variable	Parameterization
	 provider, except when born at home as intended 84 = Admission by the admission panel of an HSPH; patient not entered on the HSPH admissions waiting list (not valid for admissions after 31 March 2002) 89 = From the admissions waiting list of an HSPH (not valid for admissions after 31 March 2002) 98 = Not applicable (e.g. other maternity event) 99 = Not known
Number of non-severe CAP Baseline Period (no hospitalization or death)	Number of non-Severe CAP and Dichotomous variable (1=yes, 0=No)
Number of severe CAP in Baseline Period	Number of Severe CAP and dichotomous variable (1=Yes, 0=No)
Number of HAP in Baseline period	Number of HAP and dichotomous variable (1=Yes, 0=No)
Prior vaccination for influenza in Baseline Period	Influenza vaccination in the year prior to cohort entry (1=Yes, 0=No)
Prior vaccination for pneumonia in past 5- years	Pneumococcal vaccination in the 5-year prior to cohort entry based on recommended frequency of vaccination in the UK (1=Yes, 0=No)
Medical Research Council (MRC) dyspnea scale.	 MRC value if recorded in the year prior to 3 months following Cohort Entry Date will be included in modeling. If unknown, "unknown" would be the assigned value. Grade 1: No Dyspnea except on strenuous Exercise Grade 2: Short of breath when walking up a short hill Grade 3: Dyspnea limits walking pace (slower than others) and stops to catch breath Grade 4: Stops to catch breath after walking 100 meters (328 feet) on level ground Grade 5: Dyspnea prevents leaving house and performing Activities of Daily Living Unknown / Unavailable Collapsing of responses into fewer categories will be considered during the analysis
Entry	2007, 2008, 2009, 2010. During modeling, 2002 will be the reference year.

Additional parameterization of the data, including grouping of the count data into categories, will be considered during the creation of PS or modeling based on the distribution of the data. Details of the analysis and modeling strategy will be described in a statistical analysis plan.

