5.7.4. Multivariable Modeling

Multivariable analysis will be performed using Cox proportional hazard model with adjustment for confounders and exposures in Section 5.6 and Section 5.7.

The following outcomes will be examined:

- Severe pneumonia events (HAP and Severe CAP combined)
- All pneumonia events

Severe pneumonia events will be examined as the primary outcome. As a secondary outcome, all pneumonia events will be analyzed. The number of confounders can be supported in the modeling will be based on the total number of severe pneumonia and all pneumonia events and their distribution by treatment.

To adjust for differences confounding by severity due to differences in prescribing between ICS-containing medications and LABD, propensity scores (PS) will be utilized. The propensity score will be estimated to model the probability that a chance of a patient receiving ICS-containing medications compared with receiving LABD given a patient's observed set of baseline covariates. The logistic models used to calculate the propensity scores, all available variables in Section 5.5 (exposures) and in Section 5.6 (confounders) will be entered into the model. Propensity scores will be produced.

The PS in both groups would be evaluated for overlap, and patients with scores in the tails of the distribution that were not represented in both groups would be eliminated from the analysis. Patients with extreme PS weights (values >10) will be examined and may be removed from the analysis as their contribution would be influential and affect the model. Patients eliminated from the analysis would be described.

Multivariable analysis will be performed using Cox proportional hazard model with adjustment for the propensity score using inverse probability of treatment weighting (IPTW). This approach is more appropriate then propensity score matching when there may be effect measure modification [Stürmer, 2006]. Because of the cohort design, it is possible to adjust for confounders in the PS approach as well as include them as main effects in the model; however, it has been demonstrated that the addition of confounders with propensity scores does not contribute appreciably to the model [Rubin, 2000; Stürmer, 2006]

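### Pneumococcal vaccination (5-year look-back) and co-morbidities (whole history) are coded Yes/No although one year of records suffices for entry, so a 0 mixes absent with not observed

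*Protocol*

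**What the plan says.** Protocol Section 5.2.2, inclusion criterion 4, sets the minimum record: "Have at least one year of data prior to Cohort Entry Date". Section 5.6 then looks back further for some covariates: "For the purposes of general co-morbidity assessment and vaccination for pneumonia, a longer history will be examined". The vaccination row reads "Pneumococcal vaccination in the 5-year prior to cohort entry based on recommended frequency of vaccination in the UK (1=Yes, 0=No"). The Charlson conditions and the additional co-morbidities are taken from any time in the history and are also coded 1 or 0.

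Section 5.6 recognises that record length varies and that a difference by treatment could cause information bias. It sets this aside: "Although patients may have varying periods of history, this is not expected to be differentially recorded by treatment". No figure supports that expectation.

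Two other passages bear on the point. Year of cohort entry is a Section 5.6 covariate ("During modeling, 2002 will be the reference year"). For the propensity score, Section 5.7.4 states that "all available variables in Section 5.5 (exposures) and in Section 5.6 (confounders) will be entered into the model".

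**The concern.** A patient with between one and five years of record and no vaccination entry is coded as unvaccinated, although part of the five-year window was never seen. The same applies to a co-morbidity recorded before the current record began. Section 5.6 gives the reason itself: it justifies the longer look-back on the ground that one year may miss co-morbidities. Smoking status, GOLD stage and MRC grade each have an unknown level. The vaccination and co-morbidity indicators have none.

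This matters because the first objective in Section 4 is to estimate how risk factors relate to pneumonia requiring hospitalization, and not only to estimate the ICS effect. The Table 11 and Table 14 shells report a hazard ratio or odds ratio for pneumococcal vaccination and for each co-morbidity, and neither lists entry year or record length. False 0 codes pull those estimates towards 1 and weaken the adjustment that the covariates provide. If record length also differs by treatment, the unweighted comparisons in Tables 7 and 8 would partly reflect recording rather than patients.

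**Working it through.** **1. Table 1 (Section 5.1).** The LABD row is "354 513 703 765 715 723 972 938 994 6,677" and the ICS-containing row is "1,828 1,499 1,633 1,369 1,310 1,207 1,244 1,100 875 12,065", for 2002 to 2010 and the total. The yearly counts add to 6,677 and 12,065, together 18,742, as stated.

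**2. Mean entry year** = 2002 + Σ(years after 2002 × count) / total.
- LABD: 2002 + 31,039 / 6,677 = 2006.65
- ICS-containing: 2002 + 42,311 / 12,065 = 2005.51
- Difference: 1.14 years

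Entry in 2002–2004:
- LABD: (354 + 513 + 703) / 6,677 = 1,570 / 6,677 = 23.5%
- ICS-containing: (1,828 + 1,499 + 1,633) / 12,065 = 4,960 / 12,065 = 41.1%

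These are calendar years of entry. The protocol gives no distribution of record length, overall or by group.

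**3. Dilution of the vaccination estimate.** None of these inputs is in the protocol; all are assumptions:
- true five-year vaccination share v: 40% to 60%
- share with short records s: 10% to 40%
- share of true vaccinations visible in a short record q: 20% (one year of five) to 60% (three years of five), with vaccinations spread evenly over the window
- true hazard ratio: 0.70
- no false Yes codes, and record length unrelated to pneumonia risk

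Formulas:
- missed vaccinations m = v × s × (1 − q)
- vaccinated share of the 0 group f = m / (1 − v + m)
- observed hazard ratio = 0.70 / (1 − 0.30 f)
- share of the log hazard ratio lost = ln(1 − 0.30 f) / ln(0.70)

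| v | s | q | m | f | Observed HR | Log HR lost |
|---|---|---|---|---|---|---|
| 40% | 10% | 60% | 0.016 | 0.016/0.616 = 2.6% | 0.71 | 2% |
| 50% | 25% | 60% | 0.050 | 0.050/0.550 = 9.1% | 0.72 | 8% |
| 60% | 40% | 60% | 0.096 | 0.096/0.496 = 19.4% | 0.74 | 17% |
| 60% | 40% | 20% | 0.192 | 0.192/0.592 = 32.4% | 0.78 | 29% |

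**4. Dilution against random error.** Table 4 gives 106 severe CAP and 1 HAP, so 107 severe events. The standard error of a log hazard ratio is at best 2/√107 = 0.19. The middle row shifts the log hazard ratio by 0.028 and the last row by 0.102. With the 283 events of the all-pneumonia outcome the best-case standard error is 2/√283 = 0.12.

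**5. Possible gap in the crude tables (assumed inputs).** Suppose 30% of ICS users and 10% to 30% of LABD users have short records, q = 60%, and the true share is 40% to 60% in both groups. The recorded share is v × (1 − 0.4 s). At v = 60%, ICS users show 0.60 × 0.88 = 52.8% and LABD users 52.8% to 57.6%. At v = 40%, they show 35.2% and 35.2% to 38.4%. The artificial gap is 0 to 4.8 percentage points.

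**The case against.** A reader might infer that Table 1 contradicts Section 5.6. It does not. Later entry implies longer records only if records start at about the same date in both groups, and the protocol does not say so. Section 5.3 has practices contributing since 1987 and prescription history of up to 15 years, so even a 2002 entrant can have the full five-year window. Section 5.6 states an expectation, and Table 1 gives a reason to test it. This part of the objection stands.

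A reader might also infer a biased ICS-versus-LABD hazard ratio. The only evidence for different record lengths is entry year, and entry year is already in the propensity score. Nothing shows a difference in record length within an entry year. Even an uncontrolled vaccination gap of 45% versus 55% at a hazard ratio of 0.70 would move the treatment hazard ratio by (1 − 0.30 × 0.45) / (1 − 0.30 × 0.55) = 0.865 / 0.835 = 1.036, about 4%. Section 5.7.8 aims to exclude a margin of 2.0 for severe pneumonia. This also stands.

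Third, parameterization is left to an analysis plan that is not shown, Table 14 is exploratory, and the table footnotes allow covariates to change. That is fair as to detail. But the protocol itself fixes the Yes/No code and states the expectation about history. Weighting by a propensity score does not repair a wrong code in a reported risk factor.

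Finally, the upper figure of 29% needs 40% of patients to have short records, all at the one-year minimum. That is correct, and it should be read as an extreme.

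**Conclusion.** The point holds for the risk-factor estimates. The coding rule turns unobserved time into a No for vaccination and co-morbidities, and the expectation that history is similar by treatment is unsupported. The likely result is dilution of those estimates in Tables 11 and 14. For vaccination the loss is 2% to 29% of the log hazard ratio over the assumed inputs and about 8% in the middle. The true figure cannot be derived, because the protocol gives neither record length nor vaccination prevalence. No figure is offered for co-morbidities, which have no defined window.

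Material bias in the weighted ICS hazard ratio is not shown, since entry year probably absorbs most of any calendar-time effect. Nor do the documents support saying that the crude tables will show more vaccination or co-morbidity among LABD users; they may. The point merits a change but does not threaten the primary treatment comparison.

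**What to change.** - Tabulate years of CPRD record before the Cohort Entry Date by treatment group, and put that table in place of the Section 5.6 expectation.
- Add record length to the propensity score and to the risk-factor models behind Tables 11 and 14.
- As a sensitivity analysis, either code vaccination as not observable when none is recorded and fewer than five years of record exist, or restrict the vaccination estimate to patients with at least five years of record. The extra level belongs in a sensitivity analysis because it mixes vaccinated and unvaccinated patients and is itself defined by record length.

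Record length can be derived from existing registration dates, so no new data source is needed. The cost is a few more parameters with about 107 severe events, in a study that already expects to limit its covariates. The restricted analysis would also lose patients and events.

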5.7. Analysis

5.7.1. New User Cohort

Patients in the cohort will be described according to their COPD disease severity, treatment patterns, demographic characteristics, and co-morbidities. Treatment guidelines for COPD consider long-acting bronchodilators as monotherapy as being prescribed for patients that have less severe COPD than those who would be given an ICS as add-on to a long-acting bronchodilator.

For the primary objective, patients were required to be new users of ICS-containing medications or LABD after a one-year period of non-use. ICS are add-on therapy for LABD; therefore, new users of ICS could have ICS monotherapy or ICS/LABA as fixed dose inhaler in the one year prior to **Cohort Entry Date**.

The primary pneumonia outcomes are severe pneumonias, which are severe CAP and HAP. As there was only one patient with HAP according to the database algorithm, severe CAP and HAP were combined. The secondary outcome is all pneumonias, including HAP, severe CAP, and CAP combined. Patients can have only one pneumonia outcome (e.g., severe CAP, HAP, or non-severe HAP) in the analysis based on the first pneumonia event.

Confounders will be were selected for inclusion in the analysis based on clinical importance and are described in Section 5.7 and respiratory medications in Section 5.6. Additional information about the modeling strategy will be addressed in a statistical analysis plan.

5.7.2. Patient Follow-up Time from Cohort Entry

Patients will be followed from the date of their first eligible prescription (New User entry date) until the earliest of the following:

- date of treatment end (up to 90-day gap allowed for each inhaler),
- date of study end point (first pneumonia event of interest)
- date of transfer to a new practice / practice stops participating or CPRD ends,
- date of ICS initiation (among LABD new users)
- death or
- HES data ends (last available HES data)

As part of the primary analysis, patients will be examined for their first pneumonia (severe CAP, HAP, or non-severe CAP). For example, a patient who has HAP and then

another year has a severe CAP would be considered only for his first event, the HAP. For the analysis of severe CAP, this same patient would be censored on the start date of their HAP episode.

Each patient will have a time and "censoring" variable, which is an indicator variable (yes/no) that indicates 1 if they have had the event of interest or 0 if they are censored. Time will be calculated as the date of the event or censoring minus the cohort entry date plus 1.

Incidence rates of the pneumonia outcomes will be calculated as the number of patients experiencing an event divided by the person-years at risk. Incidence rate ratios were calculated as the incidence rate in the ICS-containing group divided by the incidence rate in the LABD group. Precision of effect estimates will be evaluated from the width of the 95% CIs.

